12.3.1.6.5. Outcome at the Time of Last Observation

The outcome of an AE at the time of last observation will be classified as:

- Recovered/resolved
- Recovered/resolved with sequelae
- Recovering/resolving
- Not recovered/not resolved
- Fatal (see [Section 12.3.1.6.6.5](#))
- Unknown

12.3.1.6.6. Serious Adverse Events

12.3.1.6.6.1. Reporting of Serious Adverse Events

Initial and follow-up SAE reports must be completed by the investigator and sent to the sponsor and the CRO within 24 hours of the first awareness of a SAE.

The investigator must complete, sign and date the appropriate SAE form and verify the accuracy of the information against corresponding source documents. No source documents are to be sent

with the SAE form. This SAE information (form) is to be sent to the CRO pharmacovigilance department, with a copy to the Aevi Genomic Medicine medical monitor by e-mail or fax at one of the methods noted below. For questions on SAE reporting, please call the drug safety helpline noted below.

12.3.1.6.6.2. Definition of Serious Adverse Event

An SAE is any untoward medical occurrence, whether considered to be related to the investigational product or not, that at any dose:

- Results in death
- Is life-threatening

NOTE: The term “life-threatening” in the definition of “serious” refers to an event in which the subject was at risk of death at the time of the event; it does not refer to an event which hypothetically might have caused death if it were more severe.

- Requires inpatient hospitalization or prolongation of existing hospitalization

NOTE: Inpatient hospitalization is defined as 24 hours in a hospital or an overnight stay. An elective hospital admission to treat a condition present before exposure to the test drug, or a hospital admission for a diagnostic evaluation of an AE, does not qualify the condition or event as an SAE. Further, an overnight stay in the hospital that is only due to transportation, organization, or accommodation problems and without medical background does not need to be considered an SAE.

- Results in persistent or significant disability/incapacity
- Is a congenital anomaly

NOTE: A congenital anomaly in an infant born to a mother who was exposed to the IP during pregnancy is an SAE. However, a newly diagnosed pregnancy in a subject that has received an IP is not considered an SAE unless it is suspected that the IP(s) interacted with a contraceptive method and led to the pregnancy.

- Is an important medical event

NOTE: Medical and scientific judgment should be exercised in deciding whether it is appropriate to consider other situations serious, such as important medical events that may not be immediately life-threatening or result in death or hospitalization but may jeopardize the subject or may require intervention to prevent one of the other outcomes listed in the definition above. Examples of such events are intensive treatment in an emergency room or at home for allergic bronchospasm, blood dyscrasias or convulsions that do not result in hospitalization, or development of drug dependency or drug abuse.

12.3.1.6.6.3. Serious Adverse Event Collection Time Frames

All SAEs, regardless of the relationship to study, are collected from the time the subject signs the informed consent until the subject's last visit (office or telephone contact). The investigator or designee must report all SAEs promptly to the CRO and Aevi Genomic Medicine medical monitor within 24 hours of first becoming aware of the event.

Any SAE(s), regardless of relationship to IP, discovered by the investigator at any interval after the study has completed must be reported to the CRO and Aevi Genomic Medicine medical monitor within 24 hours of the first awareness of the event.

12.3.1.6.6.4. Serious Adverse Event Onset and Resolution Dates

The onset date of the SAE is defined as the date the event meets serious criteria (see [Section 12.3.1.6.6.2](#)). The resolution date is the date the event no longer meets serious criteria, the date symptoms resolve or the event is considered chronic. In the case of hospitalization, the hospital admission and discharge dates are considered respectively, the onset and resolution dates of the SAE.

Any signs or symptoms experienced by the subject after signing the informed consent form, or leading up to the onset date of the SAE or following the resolution date of the SAE must be recorded as AEs.

12.3.1.6.6.5. Fatal Outcome

An outcome of “fatal” should only be selected when the AE results in death. If more than 1 AE is possibly related to the subject’s death, “fatal” outcome should be indicated for each such AE.

Any AE that results in the subject’s death must have “fatal” checked as an outcome with the date of death recorded as the resolution date. Adverse events resulting in death must be reported within 24 hours as SAEs, if not already reported as such.

For other AEs ongoing at the time of death that did not contribute to the subject’s death, the outcome should be considered “not resolved” with no resolution date recorded.

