12.3.1.6.3. Severity of Adverse Events

The severity of AEs must be recorded during the course of the event, including the start and stop dates for each change in severity. An event that changes in severity should be captured as a new event. Worsening of pre-treatment events after initiation of the investigational product must be recorded as new AEs. For example, if the subject experiences mild, intermittent headaches prior to dosing with investigational product and the headache intensity increases to moderate after the

first dose of investigational product, a new AE of moderate intermittent headaches is to be recorded in the source documents and eCRF.

The medical assessment of clinical severity of an AE will be determined using the definitions outlined in Common Terminology Criteria for Adverse Events (CTCAE), Version 4.0 (Published May 28, 2009 with Version 4.0.3 on June 14, 2010 by the US Department of Health and Human Services, National Institutes of Health, National Cancer Institute):

Grade 1	Mild; asymptomatic or mild symptoms; or clinical or diagnostic observations only; or intervention not indicated
Grade 2	Moderate; or minimal, local or non-invasive intervention indicated; or limiting age-appropriate instrumental activities of daily living (ADL)
Grade 3	Severe or medically significant but not immediately life-threatening; or hospitalization or prolongation of hospitalization indicated; or disabling; or limiting self-care ADL.
Grade 4	Life-threatening consequences; or urgent intervention indicated.
Grade 5	Death related to AE

It is important to distinguish between severe AEs and SAEs. Severity is a classification of intensity whereas an SAE is an AE that meets serious criteria as described in [Section 12.3.1.6.6.2](#).

Please refer to the above-referenced CTCAE document for full description of CTCAE terms and instrumental and self-care ADLs.

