9.2 ADVERSE EVENTS

Any untoward medical event that occurs after signing the informed consent form (ICF) is considered to be an adverse event (AE). Adverse events recorded between the time of signature of informed consent until the first dose administration will be considered baseline signs and/or symptoms.

A treatment-emergent adverse event (TEAE) is an adverse event with onset on or after the first dose administration date or an adverse event present before the first dose administration date that worsens (i.e., increases in severity) on or after the first dose administration date. TEAEs will be summarized from the first dose administration date through:

- the Safety Follow-Up/Visit 11 for subjects who completed the study or
- 28 days after the last dose administration date for subjects who discontinued prematurely from the study.

Verbatim terms used by investigators to identify AEs in the CRFs will be coded to the appropriate preferred term (PT) and system organ class (SOC) using a standardized coding dictionary (MedDRA Version 23.0 April 2020). All coding will be reviewed prior to database lock. All recorded AEs will be listed, but only TEAEs will be summarized.

Adverse events will be classified according to severity (CTCAE Grades 1-5) and relationship to study drug (not related, possibly related, or probably related). For summary tables, a "related" adverse event is one judged to be possibly related or probably related to study drug.

The following adverse event categories will be summarized by disease and cohort:

- Overall TEAEs
- TEAEs related to study drug
- TEAEs leading to discontinuation
- Serious AEs
- Severe TEAEs (Grade 3 or higher)

The number of subjects with AEs will be further summarized by SOC and PT (TEAEs, as well as related TEAEs), by PT only, and by SOC, PT and severity. Sorting will be in descending order of frequency.

If a patient has multiple occurrences of a TEAE within the same SOC and PT, only the most related or most severe will be included in the summaries.

Separate listings for all AEs, serious AEs, and AEs leading to discontinuation will be generated.

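### The SAE definition exempts every admission made to investigate an AE, planned or not, so some unplanned inpatient stays can miss 24-hour reporting and the SAE count

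*Protocol*

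**What the plan says.** Protocol section 12.3.1.6.6.2 lists among its seriousness criteria an event that "Requires inpatient hospitalization or prolongation of existing hospitalization". The NOTE under that criterion adds: "Inpatient hospitalization is defined as 24 hours in a hospital or an overnight stay". It then sets out three exclusions:

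- "An elective hospital admission to treat a condition present before exposure to the test drug";
- "a hospital admission for a diagnostic evaluation of an AE, does not qualify the condition or event as an SAE";
- an overnight stay that arises only from travel, organization or lodging problems and "without medical background does not need to be considered an SAE".

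Section 12.3.1.6.6.1 requires SAE reports to reach the sponsor and the CRO "within 24 hours of the first awareness of a SAE". Section 12.3.1.6.6.4 dates an SAE involving hospitalization from admission to discharge and makes no exception for diagnostic stays. Section 12.3.1.6.8 ties notification of regulators and sites to related, unexpected SAEs, and notification of the IRB or local authority to SAEs at the site.

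On severity, section 12.3.1.6.3 defines Grade 3 as "Severe or medically significant but not immediately life-threatening; or hospitalization or prolongation of hospitalization indicated", among other alternatives. SAP section 9.2 has a summary category for serious AEs and one for severe treatment-emergent AEs, and states: "Separate listings for all AEs, serious AEs, and AEs leading to discontinuation will be generated".

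**The concern.** The second exclusion has no limit on its scope. The words about elective admission and a condition present before exposure belong to the first exclusion. The second has its own noun and carries neither restriction. Read as written, it covers a subject admitted unexpectedly between doses for two nights while a new fever or suspected hypersensitivity is investigated.

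Safety and tolerability are the primary objective, and the cohorts are very small. Section 8.3 asks for special attention to infection, hypersensitivity and CD exacerbation, all of which could prompt an admission for work-up. An unplanned stay may well still be diagnostic when the site first learns of it, which is also when the 24-hour clock would otherwise start. Sites that weigh the criterion and the NOTE differently could classify the same event differently, and the SAP has no rule to correct this at analysis.

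**Working it through.** The plan states no figure on this point, so the check is mainly a comparison of passages.

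**Step 1. Does the stay meet the criterion?** Take an unplanned two-night admission to investigate a new AE after dosing. The definition of inpatient hospitalization in 12.3.1.6.6.2 uses duration only (24 hours or overnight) and is silent on purpose. The criterion is met.

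**Step 2. Does an exclusion remove it?**

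| Exclusion in the NOTE | Limit stated | Applies to this stay? |
|---|---|---|
| Treatment of a condition predating exposure | Elective, and pre-existing | No |
| Diagnostic evaluation of an AE | None | Yes |
| Logistical overnight stay | No medical background | No |

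Only the second exclusion removes it, and only because that exclusion has no limit.

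**Step 3. Does nearby text agree?**
- The third exclusion exempts a stay only where it has no medical background. This implies that stays with a medical background count, and a diagnostic work-up has one.
- The date rule in 12.3.1.6.6.4 puts SAE onset at admission. If a stay begins as investigation and turns into treatment, the NOTE makes it non-serious at first, while the date rule places onset on the first day. The two do not fit together.

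**Step 4. What depends on SAE status?**

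| Consequence | Location | If the event is exempted |
|---|---|---|
| 24-hour report | Protocol 12.3.1.6.6.1 and 12.3.1.6.6.3 | Not required |
| Notification of regulators and sites | Protocol 12.3.1.6.8 | Lost where related and unexpected |
| Serious AE category and listing | SAP 9.2 | Absent |
| AE recording and all-AE listing | Protocol 12.3.1.6.2; SAP 9.2 | Kept |
| Severe treatment-emergent AE category | SAP 9.2 | Kept if treatment-emergent and Grade 3 or higher |
| Individual and study stopping rules | Protocol 8.5.1 and 8.5.2 | Kept; based on CTCAE grade and liver tests |

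**Step 5. Effect of one subject.** The change in the SAE percentage is 100 × 1/n. Planned n is from the synopsis and Protocol section 8.7, and the columns are those of SAP section 5.
- Each CD cohort: 1/4 = 25.0 points
- CD total: 1/8 = 12.5 points
- UC cohort: 1/6 = 16.7 points

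This assumes that enrollment is as planned, all enrolled subjects are dosed, and the subject has no other SAE. SAP section 5 shows no column pooling CD and UC.

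**The case against.** The strongest reply is that the definition does not contradict itself. A general criterion followed by listed exceptions is a normal way to draft, and the sponsor may choose to narrow it. That stands: a reader might infer a plain contradiction, but the text shows an express exception that is too broad. The misfit lies in its scope, set against the third exclusion and the date rule.

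A reader might also infer that these events escape safety oversight altogether. The documents do not support that.
- Another seriousness criterion may apply. For a work-up admission this would usually be the important-medical-event criterion in 12.3.1.6.6.2. It depends on judgment, and its examples are cases managed without hospitalization, so it is a partial safeguard.
- The exception concerns admission to evaluate. It does not state that admission to treat an AE is exempt.
- Events remain recorded. Several of the most worrying ones at Grade 3 or higher, including hypersensitivity, opportunistic infection and bowel obstruction, are individual stopping criteria in 8.5.1. Grade 3 or greater CD exacerbations also go to the DMC under 8.5.2.
- An event that is Grade 3 but not serious is not itself an inconsistency, because 12.3.1.6.3 separates severity from seriousness.

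Two further inferences go too far. One is that regulatory expedited review is lost for every such event; section 12.3.1.6.8 requires notification of regulators only for related, unexpected SAEs. The other is that 24-hour reporting becomes weekly reporting; section 8.3 sets a weekly investigator review with safety concerns passed to the medical monitor, not a deadline for non-serious events.

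Finally, the 1/n figures would hold for any single misclassified subject. They show sensitivity, not an expected bias.

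**Conclusion.** The point holds as an over-broad exception, and it should be changed. Under the text as written, an unplanned inpatient stay to investigate a new on-treatment AE can be declared non-serious despite meeting the hospitalization criterion and its length-of-stay definition. What can be lost is prompt reporting, notification where the event is related and unexpected, and the SAE tabulation. AE capture and the grade-based stopping rules are not directly weakened.

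For each affected subject the SAE percentage shifts by 12.5 to 25.0 points, depending on the SAP column, under the assumptions in the working. The total effect cannot be estimated, because the documents do not give the frequency of such admissions. The conclusion rests on a literal reading of the NOTE and on no other seriousness criterion being invoked.

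**What to change.** In the NOTE of Protocol section 12.3.1.6.6.2, limit the diagnostic-evaluation exclusion to planned or elective admissions, so that any unplanned inpatient stay for an AE falls under the hospitalization criterion. Keep the other two exclusions. Deleting the clause would also work, but it would make a planned overnight evaluation of a minor AE an SAE, so the narrower limit fits the problem better.

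Align the date rule in 12.3.1.6.6.4 and the SAE form instructions with the revised NOTE. The SAP's SAE outputs need no change, because they follow the classification. The cost is one clause, matching edits to the date rule and form instructions, and possibly a few more SAE reports.

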12.3.1.6.7. Special Considerations

12.3.1.6.7.1. Adverse Events of Special Interest and Adverse Drug Reactions

There are no events from research to date which qualify as an adverse event of special interest. Adverse drug reactions observed in the MDGN-002 pre-clinical study as well as reactions with other biologic agents include:

[REDACTED]
[REDACTED]
[REDACTED]
[REDACTED]

[REDACTED]

Please refer to the Investigator's Brochure for further details on possible risks and adverse drug reactions.

12.3.1.6.7.2. Pregnancy

All females of childbearing potential who participate in the study should be counseled on the need to practice adequate birth control and on the importance of avoiding pregnancy during study participation. Study participants should be instructed to contact the investigator or study staff immediately if pregnancy occurs or is suspected.

Pregnancy testing will be conducted prior to administration of investigational product on every female of childbearing potential. A female who is found to be pregnant at the screening visit will be excluded from the study and considered to be a screening failure.

The investigator must report the pregnancy of any female (study participant or female partner of male study participant) who becomes pregnant during investigational product treatment or within 7 days of discontinuing the investigational product. The pregnancy should be reported within 24 hours of awareness to the CRO via the same fax and email address used for SAE reporting (see [Section 12.3.1.6.6.1](#)). The investigator should contact the designated individual(s) who receive SAE notification and record information related to the pregnancy on the designated form provided by the sponsor or its designee.

Early termination visit assessments are required as soon as possible after learning of the pregnancy. The investigator is also responsible for following the pregnancy until delivery or termination. These findings must be reported on the Exposure in Utero form/other designated form and forwarded to the designated individual(s). The event meets the SAE criterion only if it results in a spontaneous abortion or a congenital anomaly.

12.3.1.6.7.3. Abuse, Misuse, Overdose and Medication Error

Abuse, misuse, overdose or medication error involving the investigational product, as defined below, must be reported to the sponsor using the SAE reporting procedures outlined in [Section 12.3.1.6.6.1](#) whether or not they result in an AE or SAE. The 24-hour reporting period from time of first awareness does not apply to an abuse, misuse, overdose, or medication error event(s) unless the abuse, misuse, overdose, or medication error event results in a SAE.

Abuse	Persistent or sporadic intentional intake of IP when used for a non-medical purpose (for example, to get high, for potential psychoactive effects) in a manner that would be detrimental to the individual and/or society
Misuse	Intentional use of IP other than as directed or indicated at any dose. This includes where IP is not used as directed at the dose prescribed in the protocol.
Overdose	Intentional or unintentional intake of a dose of IP exceeding the dose prescribed to the subject as part of the study.
Medication error	Error made in prescribing, dispensing, administration and/or use of IP. A medication error is reportable to the sponsor or its designee if it involves: 
• Administration and/or use of an unassigned treatment (for example, incorrect IP kit used by subject)• Administration and/or use of expired IP

IP=investigational product

NOTE: An abuse, misuse, overdose or medication error event can meet more than 1 category.

Missing doses are not considered medication error events and do not need to be reported.

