8.2.3. Safety Follow-up Visit

Approximately 28 days after the final dose, subjects will have a safety follow-up visit. The safety follow-up visit will be conducted in the clinic with the subject. Any AEs that occurred in the time since the subject's last MDGN-002 dose will be recorded, along with any concomitant medication use.

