10. TREATMENT OF SUBJECTS

10.1. Description of Investigational Product

A description of the investigational product is provided in [Section 11.1](#)

Subjects in each dose cohort will receive the investigational product as a single SQ injection in the abdomen in a zone of 4 to 10 cm from the umbilicus with the injection site rotated with each subsequent dose. The dose of MDGN-002 will be administered on Days 0, 14, 28, and 42. After Day 0, injections must occur within \pm 3 days of the scheduled 14-day intervals.

Subjects in the first dose cohort will receive MDGN-002 1.0 mg/kg for the entire 8-week, open-label treatment period. Data from this cohort will be reviewed by the Data Monitoring Committee as described in [Section 8.4](#) before subjects in the second dose cohort can be treated.

Eligible subjects in the second dose cohort will receive MDGN-002 3.0 mg/kg for the entire 8-week, open-label treatment period. Data from the second cohort will be reviewed, as described in [Section 8.4](#), after all subjects have completed the treatment period and its associated assessments.

Any quality issue noticed with the receipt or use of an investigational product provided by the sponsor (deficiency in condition, packaging, appearance, pertaining documentation, labeling, expiration date, etc.) should be promptly communicated to the sponsor, who will investigate.

A potential defect in the quality of investigational product provided by the sponsor may be subject to initiation of a recall procedure by the sponsor. In this case, the investigator will be responsible for promptly addressing any request made by the sponsor, in order to recall the investigational product and eliminate potential hazards.

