10.2.3. Contraceptive Methods

Sexually active study participants must agree to the use of effective contraceptive methods during the study and for the defined period after the end of study visit. Approved methods require double barrier according to the following algorithm: condom plus intra-uterine device or condom plus hormonal contraceptive. Should any subject be sterilized, the procedure for sterilization is required to have been completed more than 3 months prior to study screening visit.

A sexually active male participant must use one of the above-described double barrier contraceptive methods during the study and for 3 months after the end-of-study visit. A sexually

active female participant must use one of the above-described double barrier contraceptive methods during the study and for 1 month after the end-of-study visit.

Male subjects must also have to agree not to donate sperm for the duration of the study and for up to 3 months after the end-of-study visit.

Study participants who are abstinent at the time of study entry must agree to use the approved methods described in this section should they become sexually active during the study.

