12.1.7. Safety Follow-Up

12.1.7.1. Visit 11 (Day 84 [± 3 days])

Subjects will return to clinic 28 days (± 3 days) after Visit 10 or the early termination visit for a safety follow-up visit, as appropriate. Subject will have blood collected for plasma MDGN-002 concentration, PK and ADA analyses. Any concomitant medications and newly occurring AEs since the last visit will be recorded. In addition, ongoing AEs from the previous visit will be assessed and any change in their status will be recorded.

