12.2. Study Duration

The overall study duration is expected to be approximately 26 weeks (including up to 14 weeks of screening [inclusive of wash-out of up to 12 weeks, if required], 56 days of open-label treatment, and a follow-up visit approximately 28 days after the final dose of investigational product).

The planned sequence and maximum duration of the study periods will be as follows:

1. Screening period: approximately 2 weeks
2. Wash-out period, if applicable: Up to 12 weeks from the subject's last dose of biological treatment
3. Open-label treatment period: 56 days (beginning on Day 0 with doses administered q14 days)
4. Follow-up: 28 days after the last dose of investigational product.

The maximum study duration for each subject is approximately 26 weeks.

The maximum treatment duration for each subject is approximately 56 days, with SQ injections beginning on Day 0 and continuing every 14 (± 3) days through Day 42.

Note: Extensions of the screening window to accommodate clinical laboratory re-testing timeframes (excluding endoscopy with biopsy) are permitted as agreed with medical monitor.

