13.1.2. Statistical Analyses

Analyses of efficacy will focus on the Efficacy Population. Results of endpoints (e.g., CDAI, SES-CD, abdominal pain and loose/watery stool frequency and IBD-Q (CD only; Modified Mayo Score, stool frequency, rectal bleeding, endoscopic appearance, and IBD-Q (UC only) will be summarized by visit for each cohort, both as raw scores and the change from baseline value. For CD, the CDAI individual and total scores will be derived programmatically using recorded data from patient diary, responses to CDAI questions, laboratory tests, and physical exam results.

For UC, the Modified Mayo Score individual and total scores will be derived programmatically using recorded data from patient diary and endoscopy results. Quantitative endoscopy and biopsy results will also be summarized for both the Baseline and End of study visits.

Analyses of safety data will be focused on the Safety Population (as defined in [Section 13.1.1](#)).

Safety variables include treatment-emergent AEs (TEAEs), clinical laboratory results, vital signs measurements, ECG results, and physical examination findings.

Adverse events will be coded using Medical Dictionary for Regulatory Affairs (MedDRA). TEAEs are defined as any AE having first onset or worsening in severity after the first administration of IP. TEAEs will be classified by system organ class (SOC) and preferred term and summarized by the number of subjects reporting each event for each cohort and overall.

For clinical laboratory tests, descriptive summaries of actual (absolute) values and change from baseline values will be presented by cohort for each study visit.

Vital signs (systolic and diastolic blood pressure, pulse, and respiratory rate) and ECG results will be summarized by visit and cohort using appropriate descriptive statistics.

Data in this open-label study will be monitored continually and may be analyzed at any time.

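### The duty to report pregnancies closes about 51 days (female subjects) or 111 days (partners) before the protocol's own contraception period ends

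*Protocol*

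**What the plan says.** Protocol 12.3.1.6.7.2 (Pregnancy) requires the investigator to report, within 24 hours of awareness, the pregnancy of a female subject or a male subject's female partner "who becomes pregnant during investigational product treatment or within 7 days of discontinuing the investigational product". It then makes the investigator responsible for following the pregnancy to delivery or termination and for recording the findings on an in-utero exposure form. The same section has subjects told to contact the site at once if pregnancy occurs, with no time limit.

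Protocol 10.2.3 sets the contraception periods. Sexually active men must use "double barrier contraceptive methods during the study and for 3 months after the end-of-study visit"; sexually active women must use "double barrier contraceptive methods during the study and for 1 month after the end-of-study visit".

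Dosing is fixed in Protocol 10.1: "The dose of MDGN-002 will be administered on Days 0, 14, 28, and 42". Protocol 12.2 adds: "The maximum treatment duration for each subject is approximately 56 days". SAP 5.3 gives a half-life of 18.0 to 27.0 days.

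Neither document defines discontinuing the product or the end-of-study visit for these purposes. SAP 6.2 comes closest to the second: it counts a subject as having completed the study on completing the follow-up visit. Protocol 8.1, Protocol 12.1.7.1 and SAP 2 place that visit (Visit 11) at Day 84.

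**The concern.** The two sections do not fit together. Section 10.2.3 treats conception as something to prevent for weeks or months after section 12.3.1.6.7.2 has stopped requiring the investigator to report it. The 7 days work as a cut-off on the date of conception, and they amount to only 0.26 to 0.39 of a half-life (7/27 to 7/18).

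What is at stake is the record of in-utero exposure, in a trial whose primary objective is safety. Following a pregnancy to its outcome is how that record is made. A female subject could conceive after the cut-off but before her last study visit, where drug concentration is still sampled. If the pregnancy were uncomplicated, the rule as written would place no clear duty on the investigator to report or follow it. Adverse outcomes alone are hard to interpret without the normal ones.

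**Working it through.** The plan states no gap in days, so there is no figure to reproduce; the check is calendar arithmetic on nominal protocol days (first dose = Day 0). I assume 1 month = 30 days and 3 months = 90 days.

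**Inputs**
- Discontinuing: Day 42 if it means the last injection (Protocol 10.1); Day 56 if it means the end of the treatment period (Protocol 12.2).
- End-of-study visit: Day 84 (Visit 11), supported by SAP 6.2 with Protocol 8.1, Protocol 12.1.7.1 and SAP 2. Protocol 12.1.7.1 counts the 28 days from "after Visit 10 or the early termination visit for a safety follow-up visit". Two weaker readings exist. Day 70 follows from Protocol 8.2.3, "Approximately 28 days after the final dose, subjects will have a safety follow-up visit" (42 + 28). Day 56 follows from Protocol 13.1.2, "Quantitative endoscopy and biopsy results will also be summarized for both the Baseline and End of study visits", because the final endoscopy is at Visit 10.
- Half-life 18 to 27 days (SAP 5.3).

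**Formulas**
- Reporting closes = discontinuation day + 7.
- Contraception ends = end-of-study day + 30 (women) or + 90 (men).
- Gap = contraception end − reporting close.

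| Discontinuation | Reporting closes | End-of-study visit | Contraception ends (F / M) | Gap in days (F / partners) |
|---|---|---|---|---|
| **Day 56** | **Day 63** | **Day 84** | **114 / 174** | **51 / 111** |
| Day 56 | Day 63 | Day 70 | 100 / 160 | 37 / 97 |
| Day 56 | Day 63 | Day 56 | 86 / 146 | 23 / 83 |
| Day 42 | Day 49 | Day 84 | 114 / 174 | 65 / 125 |
| Day 42 | Day 49 | Day 70 | 100 / 160 | 51 / 111 |
| Day 42 | Day 49 | Day 56 | 86 / 146 | 37 / 97 |

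The bold row is the best-supported reading. On it, reporting also closes 84 − 63 = 21 days before the last study visit. Allowing ±3-day visit windows and calendar months (28–31 or 89–92 days) widens the overall ranges to 21–75 days (female subjects) and 82–136 days (partners). The gap is positive throughout.

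**Drug remaining in a dosed female subject.** Share of the drug present after the last dose = 0.5^(d / half-life), with d counted from Day 42 and first-order decline assumed:
- Day 63 (d = 21): 0.445 at 18 days, 0.583 at 27 days, so about 45–58%.
- Day 84 (d = 42): 0.198 and 0.340, so about 20–34%.
- Day 114 (d = 72): 0.0625 and 0.157, so about 6–16%.

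The share falls to one half on Day 42 + 18 = 60 or Day 42 + 27 = 69.

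**The case against.** The strongest reply is that section 12.3.1.6.7.2 sets a mandatory minimum and forbids nothing. Subjects are told to call if pregnancy occurs. Any SAE found after the study is reportable without time limit (12.3.1.6.6.3). That covers spontaneous abortion and congenital anomaly (12.3.1.6.7.2), and also a pregnancy suspected to result from an interaction between the product and a contraceptive (12.3.1.6.6.2). No text requires the reporting and contraception windows to match. All of this stands, and it narrows the point. A reader might infer that later pregnancies would be lost altogether; the documents do not support that. But the instruction to call binds the subject and the SAE route covers serious events. Neither gives the investigator a duty to report an uncomplicated later pregnancy and follow it to outcome.

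A second reply concerns exposure. A reader might infer that a woman conceiving in the uncovered window would typically still carry half or more of the drug. The arithmetic does not support this: with a Day 63 cut-off, that holds for none of the 51 days at an 18-day half-life and for about 6 of them (Day 63 to 69) at 27 days. The model also ignores the absorption phase of a subcutaneous dose, and SAP 5.3 gives the half-life without population, dose or route. The percentages are illustrations and say nothing about a partner's exposure.

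Third, the readings of the undefined terms are not equally good. The Day 56 and Day 70 end-of-study readings rest on loose wording elsewhere and yield to the SAP's definition of completion and the visit schedule. That is why one gap is put first and the range is kept as a sensitivity check.

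**Conclusion.** The mismatch holds on every reading. On the best-supported one, the investigator's duty covers conceptions to Day 63, while contraception is required to about Day 114 for female subjects and Day 174 for male subjects: gaps of about 51 and 111 days, with overall ranges of 23–65 and 83–125. This rests on nominal visit days, 30-day months, treatment taken as the 56-day period and Visit 11 as the end-of-study visit.

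For female subjects, the half-life adds weight: meaningful drug may remain at the cut-off and at the last visit. For partners, the point rests only on the inconsistency with section 10.2.3. The documents available give no fetal-risk threshold, so the size of any risk is unknown.

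Severity is minor. With about 14 subjects and two contraceptive methods required, few pregnancies are expected, and no planned analysis changes. It is a cheap improvement to safety capture.

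**What to change.** Amend Protocol 12.3.1.6.7.2 to require reporting, and follow-up to outcome, of any pregnancy in a subject or partner conceived from the first dose to the end of the contraception period in 10.2.3. State in 10.2.3 that the end-of-study visit is Visit 11: Day 84, or 28 days after early termination. The window then runs to 1 month after that visit for female subjects and 3 months after it for partners. Leave the contraception periods as they are.

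The cost is one protocol amendment, with investigator signature and IRB approval (Protocol 14.6), and a few follow-up contacts. No visit is planned after Visit 11, so later reports would depend on subjects contacting the site, as they are already told to do.
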